### ***Synopsis***

Insomnia is the most common sleep disorder affecting millions of adults and is linked to daytime impairment. Insomnia is typically thought of as a symptom, secondary to a primary disorder, and often goes untreated for years. Medication (over the counter or prescription) and sleep hygiene are typical insomnia symptom treatments but they do not address the cause of the insomnia. Newer guidelines view insomnia as a co-morbid disorder needing independent treatment. Recent research has discovered high rates of sleep-disordered breathing (SDB) among insomnia patients; this co-morbid pairing is referred to as "complex insomnia." Several studies have revealed that treatment of SDB decreases insomnia.

This study will determine which of two different types of positive airway pressure (PAP therapy) modes are more effective in reducing sleep breathing events in chronic insomnia patients and in decreasing insomnia severity. Patients presenting to the clinic with a primary complaint of insomnia will be potential participants for this study. Following diagnostic polysomnography (PSG) testing, insomnia patients diagnosed with SDB and meeting inclusion criteria will be randomized to a PAP treatment arm, CPAP or ASV. No experimental devices will be used in this study, both CPAP and ASV are FDA approved for treatment of SDB and are in wide use in the USA. Participants will complete a series of three titration studies with their assigned PAP mode and attend a minimum of five clinical follow-up appointments over a 14-16 week timeframe. Titration PSG studies will assess PAP pressure needs to ensure that patients are receiving optimal therapy at all times during this study. Clinical follow-up visits occur every two weeks at which time objective data download information and subjective measures will be collected. PAP adaptation barriers will be addressed as they arise during the study, because it is important that participants are able to use PAP therapy nightly during participation in this protocol. Baseline scores on insomnia severity, sleep quality, subjective insomnia parameters, sleep related impairment, and quality of life will be compared to outcome measures at the 4 month mark. Pre-treatment and post-treatment objective improvements on sleep studies will also be compared including sleep breathing indices, sleep consolidation indices, and objective data download information.

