Finally, another and equally large barrier to any successful RCT with PAP-T for chronic insomnia patients involves the use of a PAP-T placebo device. By the nature of insomnia and by the expectation that a useful insomnia treatment should be demonstrated over a minimum of 3 to 6 months, in our opinion it is unreasonable that any insomnia patient, let alone any institutional review board would accept the notion of using sham PAP therapy for 3-4 months.

Thus, given the current standard of care in the field of sleep medicine, the most pragmatic initial PAP therapy RCT protocol would involve the use of fixed CPAP as the control in comparison to the experimental group with advanced PAP technology, which from our experience would be an ASV device.

We hypothesize the following:

- (1) The use of ASV PAP therapy would prove superior to standard fixed CPAP in decreasing insomnia severity on a validated insomnia research scale, increasing sleep efficiency by self-report and objectively on PSG, and improving additional subjective and objective markers of sleep quality.

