### **Secondary Endpoint Objectives:**

- Objective improvements on sleep studies
  - Sleep breathing indices (AHI, RDI)
  - Sleep consolidation indices (SE%, REM%, REM min)
  - Objective Data Download (% compliance; % use, AHI, flattening %)
- Subjective Validated Psychometric Instruments
  - Sleep related impairment (ESS, VAS-F, VAS-S, III, FSS, SDB-6)
  - Quality of Life/Impairment (FOSQ-10, QLESQ, HSCL)

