#### *Final Dataset of RCT*

The final dataset comprises those participants in 14 to 16 week window and will be used for the primary research paper for this study to address the comparison between CPAP and ASV in the treatment of SDB events among chronic insomnia patients as well as the resultant outcomes from these distinct therapies.

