#### **Data Analysis:**

Primary analysis is a repeated measures ANOVA to test for a group by time interaction with calculated effect sizes (Cohen's d or Hedges g). The initial analysis will be with a single ISI score. Both study completers and intent-to-treat (ITT) analyses will be conducted, albeit this is an efficacy study therefore the ITT is not necessarily germane to the focus of the work.

Several other variables will be analyzed in similar fashion (breathing event indices, sleep consolidation indices, sleep diary metrics, addition secondary variable measurements). As indicated by post-hoc factor analyses, we may also conduct more advanced multi-variate analyses.

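### Hypothesis 1 claims ASV superiority on a secondary variable (PSG sleep efficiency) and on unnamed further markers, and no rule stops such a claim when ISI is null

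*Combined protocol and SAP*

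**What the plan says.** The hypothesis at the end of Background opens with insomnia severity: "The use of ASV PAP therapy would prove superior to standard fixed CPAP in decreasing insomnia severity on a validated insomnia research scale". The same sentence goes on to claim superiority in "increasing sleep efficiency by self-report and objectively on PSG, and improving additional subjective and objective markers of sleep quality".

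The endpoint lists rank these items differently. Primary Endpoint objectives has six measures: ISI, the diary sleep quality rating, the global morning rating, and diary SOL, WASO and SE. Self-reported sleep efficiency is therefore primary. PSG sleep efficiency is under Secondary Endpoint Objectives, in "Sleep consolidation indices (SE%, REM%, REM min", and AHI and RDI are secondary as well.

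Breathing events nevertheless come first in the study question. The Synopsis asks "which of two different types of positive airway pressure (PAP therapy) modes are more effective in reducing sleep breathing events in chronic insomnia patients", and only then turns to insomnia severity. Purpose & Clinical Impact uses the same order. Final Dataset of RCT describes the "primary research paper for this study to address the comparison between CPAP and ASV in the treatment of SDB events among chronic insomnia patients".

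Data Analysis starts with a single ISI score and then says: "Several other variables will be analyzed in similar fashion (breathing event indices, sleep consolidation indices, sleep diary metrics, addition secondary variable measurements". It adds: "As indicated by post-hoc factor analyses, we may also conduct more advanced multi-variate analyses". The only significance level in the document is two-tailed .05, under Power Analysis and Sample Size, where the effect size concerns insomnia severity.

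**The concern.** A secondary endpoint can go without multiplicity adjustment when it only supports the primary result. Here the one stated hypothesis asserts superiority on a secondary variable and on a set with no boundary, so the secondary label does not limit what may be claimed. Taking ISI first fixes an order of work. It does not say what follows if ISI shows no difference.

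Under the plan as written, a trial with a null ISI could report p<.05 on PSG sleep efficiency, or on another measure presented as a marker of sleep quality, as confirming part of hypothesis 1. A difference in AHI or RDI could be reported as answering the leading study question. Neither conclusion would carry the error rate or power in the sample-size paragraph, which refer to insomnia severity. The option of multivariate analyses guided by a post-hoc factor analysis widens the choice further.

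**Working it through.** **The plan's own figure.** Inputs from Power Analysis and Sample Size: net effect d about 0.80, two-sided .05, 25 per group. Power is 0.807 by the normal approximation and 0.791 by the t test, so the plan's .80 is reproduced for one insomnia-severity comparison. (The plan's 26 per group at .90 is not reproduced: these inputs need 33 by the normal approximation and 34 by the t test. That is a separate matter and does not affect this point.) The documents state no error rate for a family of tests.

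**Count of secondary variables**, from Secondary Endpoint Objectives:

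- PSG breathing: AHI, RDI (2)
- PSG consolidation: SE%, REM%, REM min (3)
- Device download: % compliance, % use, AHI, flattening % (4)
- Impairment: ESS, VAS-F, VAS-S, III, FSS, SDB-6 (6)
- Quality of life: FOSQ-10, QLESQ, HSCL (3)

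The PSG variables number 2 + 3 = 5, and the whole list 2 + 3 + 4 + 6 + 3 = 18. This is a minimum, since HSCL has two parts and most measures are repeated at several visits.

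**Error in ASV's favour.** The hypothesis is directional, so the relevant event is a false result favouring ASV. At two-sided .05 that is .025 per test. For k independent tests the chance of at least one is 1 − 0.975^k:

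- k = 5: 1 − 0.975^5 = 0.119
- k = 18: 1 − 0.975^18 = 0.366

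For correlated tests I took equicorrelated normal statistics, Z_j = √ρ·G + √(1−ρ)·E_j. The chance is then 1 − ∫ φ(g)·Φ((1.96 − √ρ·g)/√(1−ρ))^k dg.

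| Correlation ρ | 5 PSG variables | 18 secondaries |
|---|---|---|
| 0 | 11.9% | 36.6% |
| 0.3 | 10.5% | 26.3% |
| 0.5 | 9.1% | 19.9% |
| 0.7 | 7.4% | 13.9% |
| 0.8 | 6.4% | 10.8% |

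One test gives 2.5%. At ρ = 0.5 the ratio is 9.1/2.5, about 3.7, for the PSG set and 19.9/2.5, about 8, for the full list.

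**Effect of a gate.** If ISI is tested at two-sided .05 and any further formal claim is tested only after ISI is significant, in a fixed order or with Holm, the chance of any false claim in that family is at most 5%. The power of the ISI test stays at 0.79.

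**The case against.** The strongest reply is that the plan does rank its variables. It separates primary, secondary and tracking measures, bases its power on insomnia severity, analyses ISI first and calls the factor analysis post-hoc. Leaving secondary endpoints unadjusted in a 50-patient trial is common. All of this is true, and it means the plan has an ordering. But no sentence turns the ordering into a condition, and the hypothesis reaches past the primary list.

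Four stronger readings are tempting, and the documents do not support them.

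- **That the protocol claims ASV superiority on breathing events.** The Synopsis asks without direction which mode is more effective. Purpose & Clinical Impact and Final Dataset of RCT speak of relevance and comparison, and hypothesis 1 does not name breathing events.
- **That a false superiority claim is more probable than not.** The 60% obtained for 18 independent tests (1 − 0.95^18) includes results favouring CPAP. In ASV's favour the rate stays below one half even for all 24 primary and secondary measures under independence (1 − 0.975^24 = 45.5%). Most of the 18 are impairment, quality-of-life or download measures, which are not obviously markers of sleep quality, so the five-variable figure is closer to the hypothesis.
- **That every part of the hypothesis must succeed, with a loss of power.** No section requires this, and d = 0.80 is given only for insomnia severity.
- **That a breathing difference without an ISI difference is expected at the endpoint.** Titration #1 (Initial) ties under-treatment on CPAP to the titration and early adaptation, while Titration #3 (Final) makes the main objective comparison when adaptation should be near its best. A true breathing difference would also not be a chance finding. The problem there would be which question it answers.

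**Conclusion.** The point holds as a gap between claim and endpoint rank. Hypothesis 1 asserts ASV superiority on PSG sleep efficiency and on an open-ended set, and following the plan permits that conclusion after a null ISI.

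The chance of a false ASV-favouring result rises from 2.5% for one test to about 9% over the five PSG variables (6% to 12%), and to about 20% over all 18 secondaries (11% to 37%). These figures rest on three assumptions: no true differences on the variables counted; the .05 level applied to each secondary variable, which is inferred because the plan states it only in the insomnia-severity sample-size paragraph; and a common correlation of 0.5, with range 0.8 to 0, because the documents give none.

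The inflation is material, and the plan should be changed. The defect lies in what may be concluded; the ISI comparison itself is not affected.

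**What to change.** 1. In the hypothesis (Background) and in Data Analysis, make ASV versus CPAP on ISI change from baseline to 4 months the one confirmatory test, at two-sided .05.
2. Amend Primary Endpoint objectives to match. Otherwise five other measures, self-reported sleep efficiency among them, stay listed as primary and contradict the new hypothesis. They can become key secondary endpoints or be tested after ISI.
3. If PSG sleep efficiency or a named breathing index (AHI or RDI) is to carry a formal claim, test it only if ISI is significant, in a fixed order or with Holm.
4. Report all other secondary variables, and anything selected through the factor analysis, as supportive or exploratory, with between-arm differences and 95% confidence intervals and no superiority wording.

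The cost is protocol text only: no added patients, visits or data. Two things are given up. A secondary p<.05 with a null ISI could no longer be reported as showing superiority, and five measures would lose equal standing with ISI.

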### ***Patient Selection***

All adult, chronic insomnia patients presenting at Maimonides Sleep Arts & Sciences, Ltd (MSAS) are potential candidates for this study. This sleep center serves the greater Albuquerque, NM area. The population consists of treatment seeking patients for a variety of sleep disorders. The estimated number of potential participants during any given month is 5 to 10; the recruitment and patient participation should be completed over a 12 to 18 month period.

### ***Purpose & Clinical Impact***

The purposes of this study are to: (1) determine the clinical relevance of different forms of positive airway pressure (PAP) therapy in treatment of sleep breathing events in chronic insomnia patients with co-morbid sleep-disordered breathing; (2) measure the impact of such treatment on insomnia severity; and (3) demonstrate a potential role for this new therapeutic pathway for chronic insomnia patients.

### ***Protocol***

#### **Abstract:**

[figure not shown]
As presented in the in-depth Background material, emerging research strongly indicates the need for an RCT to evaluate the role of PAP therapy in the treatment of chronic insomnia. This study, succinctly summarized in the following two flow charts (A. Patient Encounters; B. Patient Timetable) proposes this project to test standard CPAP therapy versus a more advanced form of CPAP therapy known as adaptive servo-ventilation (ASV). During a 14-16 week period, two groups of approximately 25 patients each will use either CPAP or ASV, and their specific sleep outcomes and related variables will be tracked daily or every two weeks to provide data for a final comparative analysis between the two groups. The summary of endpoint objectives (page 10) following the two flow charts describes the primary and secondary outcomes for this study.

Flowchart A: Patient Encounters in Protocol Steps. This chart describes the entry of the patient into the study after confirmation of the diagnosis of SDB.

[figure not shown]
Flowchart B: Patient Timetable and Protocol Steps. This chart describes estimated time commitment for each participant once the diagnosis of SDB is confirmed.

**Flow charts and timetables:**

Flow chart A: Patient Encounters in Protocol Steps

Flow chart B: Patient Timetable and Protocol Steps

## **Summary of Endpoint Objectives:**

### **Primary Endpoint objectives:**

- Change in insomnia severity from baseline to 4 months as measured by the Insomnia Severity Index (ISI)
- Sleep Diary sleep quality rating (8 point Likert scale)
- Global Morning Rating of Nightly Sleep (0-100% scale)
- Change in prospective sleep log data for insomnia parameters (SOL, WASO, SE)

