### **Power Analysis, Sample Size Data Analysis**

#### **Power Analysis and Sample Size:**

Based on our description in the background (see page 6), our work with ASV anticipates an effect size of at least 1.40 to 1.50 change in insomnia severity with ASV PAP therapy. Whereas, based on our clinical experience we presume that the effect of CPAP on insomnia would yield an effect size range between 0.50 and 0.70. Thus, the average net effect between ASV and CPAP use would be ~0.80 effect size. Using a resource specific to clinical research(77)in order to calculate power and sample size estimates, we used a beta of .90 for two tailed significance testing at .05 which arrived at 26 patients per group, or a total sample of 52. Therefore, using the less stringent criteria of beta .80, we believe our sample size allotments of 25 per group or 50 total should prove more than sufficient for this protocol.

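### Six variables are labelled primary with no rule for which decides, while the sizing and the lead analysis use ISI alone; the two statements should be reconciled by naming ISI as the single primary endpoint

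*Combined protocol and SAP*

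**What the plan says.** The Abstract of the Protocol section points the reader to the Summary of Endpoint Objectives for the primary and secondary outcomes, so that summary is the governing statement. Its primary list has four bullets: change in ISI from baseline to 4 months, the diary sleep quality rating, "Global Morning Rating of Nightly Sleep (0-100% scale"), and "Change in prospective sleep log data for insomnia parameters (SOL, WASO, SE"). The last bullet holds three variables, which makes six in all. They are not ranked.

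Power Analysis and Sample Size works from one variable. The ASV experience "anticipates an effect size of at least 1.40 to 1.50 change in insomnia severity", and for the test itself "we used a beta of .90 for two tailed significance testing at .05". The effect sizes come from the ISI results described in the Background.

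Data Analysis makes the group-by-time interaction in a repeated measures ANOVA the primary analysis and adds: "The initial analysis will be with a single ISI score". It continues: "Several other variables will be analyzed in similar fashion (breathing event indices, sleep consolidation indices, sleep diary metrics, addition secondary variable measurements"). Breathing and consolidation indices are secondary in the endpoint summary; the diary metrics in the same list are primary there.

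The single hypothesis at the end of the Background joins insomnia severity, sleep efficiency (self-reported and on PSG) and further markers of sleep quality with the word 'and'. It does not say which of them must be significant.

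**The concern.** The endpoint summary gives six variables equal standing. The sizing and analysis sections treat one as the lead and put the other five beside secondary variables. Both cannot describe the same decision, and no sentence says which governs. 'Initial' in Data Analysis fixes a sequence; it does not make later tests conditional on the first.

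The practical risk is in reporting. Suppose ISI shows no significant difference between ASV and CPAP but diary WASO reaches p < 0.05. Under the endpoint summary, that is a significant result on a primary endpoint, and nothing in the plan bars calling it a primary success. With five such extra chances, the error rate of a claim made that way is above the stated .05.

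**Working it through.** **1. The plan's own figure.** Inputs from Power Analysis and Sample Size: net effect d about 0.80, two-tailed .05, 26 per group at what is called a beta of .90 (read as 90% power), then 25 per group at .80.

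Normal approximation, n per group = 2(z₁₋α/₂ + z_power)² / d²:
- 90% power: 2(1.960 + 1.282)² / 0.64 = 32.8, so 33 (34 by the two-sample t-test).
- 80% power: 2(1.960 + 0.842)² / 0.64 = 24.5, so 25 (26 by the t-test).

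The 26 per group therefore does not reproduce at 90% but matches 80%. With 25 per group, t-test power is 79%, close to the stated fallback. This is a side observation. What matters here is that the calculation has one variable and one test at .05.

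**2. Number of primary variables.** ISI (1) + sleep quality rating (1) + Global Morning Rating (1) + SOL, WASO, SE (3) = 6, of which 5 are diary variables.

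**3. False-positive risk under each possible rule.**
- ISI alone decides: 5%.
- All six must be significant: at most 5%, since the joint event cannot be likelier than any single one.
- Any one of six suffices, independent tests: 1 − 0.95⁶ = 26.5%.
- Any one of six suffices, correlated tests: computed below.

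Model for the last rule, with no true difference on any variable: Z_j = √ρ·U + √(1−ρ)·e_j for j = 1 to 6, with U and e_j independent standard normals. The common correlation ρ is an assumption. For a given U = u, let g(u) be the chance that one test has |Z| ≤ 1.96, and h(u) the chance that Z ≤ 1.96, with positive Z favouring ASV. Averaging over U:
- any of six, either direction: 1 − E[g⁶]
- any of six, favouring ASV: 1 − E[h⁶]
- at least one diary test significant, ISI not, either direction: E[g(1 − g⁵)]
- at least one diary test favouring ASV, ISI not significant: E[g(1 − h⁵)]

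| ρ | Any, either direction | Any, favouring ASV | Diary only, either direction | Diary only, favouring ASV |
|---|---|---|---|---|
| 0 | 26.5% | 14.1% | 21.5% | 11.3% |
| 0.3 | 24.1% | 12.2% | 19.1% | 9.6% |
| 0.5 | 20.7% | 10.4% | 15.7% | 7.9% |
| 0.7 | 16.4% | 8.2% | 11.4% | 5.7% |
| 0.9 | 10.8% | 5.4% | 5.8% | 2.9% |

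The baseline for one test is 5% in either direction and 2.5% in favour of ASV. The last column is the event described in the concern: a false claim for ASV resting on the diary alone.

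**4. What control costs ISI.** Two-sample t-test, d = 0.80 taken as the standardised difference in change, 25 per group:
- ISI as sole or first test at 0.05: 79%, unchanged.
- Equal split, 0.05/6 = 0.0083: 53%; about 40 per group would be needed for 80%.

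The t-test matches the planned group-by-time test when that test uses two time points, baseline and final.

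**The case against.** The best case for the plan is that ISI already leads. The trial is sized on insomnia severity, the analysis opens with a single ISI score, and diary metrics appear among other variables in a list that includes secondary ones. On that reading the error is 5% and nothing is inflated. The hypothesis also fits a rule under which any one variable suffices poorly, because it joins its outcomes with 'and'.

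Most of this stands. It is the better-supported reading, and it is why the percentages above are conditional. It does not close the gap: no sentence withdraws the primary label from the diary variables, makes their tests depend on ISI, or turns the hypothesis into a success rule.

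Two stronger readings are tempting. A reader might infer that this trial has a false-positive risk of 16–24%. The documents do not support that: no passage says any one variable is enough, no correlations are given, and those figures count errors favouring either arm. The risk of a false claim for ASV is about half as large.

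A reader might also attach the choice between completers and intent-to-treat, since Data Analysis runs both and adds "albeit this is an efficacy study therefore the ITT is not necessarily germane to the focus of the work". That is a separate question. The sentence "The final dataset comprises those participants in 14 to 16 week window and will be used for the primary research paper for this study" may only separate the trial data from the six-month follow-up. The greater intolerance expected on CPAP is described as handled by down-titration, not as leading to dropout, so different selection of completers by arm would be an inference.

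**Conclusion.** The inconsistency is real. Six variables are called primary in one place; elsewhere one is sized and led with, and no decision rule connects them. The plan should be changed, but it does not commit the sponsor to an inflated error rate.

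The size depends on the rule. It is at most 5% if ISI alone decides or all six must succeed. If any one sufficed at two-sided 0.05, it would be 16–24% in either direction for common correlations of 0.7 to 0.3, or 8–12% in favour of ASV against 2.5% for a single test. A diary-only false positive favouring ASV with ISI not significant would be about 6–10%. The correlation range and the equal-correlation model are assumptions; the table shows how the figures move outside that range.

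**What to change.** Before any outcome data are seen:

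1. In the primary endpoint list, name change in ISI from baseline to the week 14–16 visit as the single primary endpoint, tested at two-sided 0.05. This matches the sizing and lead analysis.
2. State that superiority of ASV is concluded only if the ISI comparison is significant in its favour.
3. Test the five diary variables in a stated fixed order after a significant ISI, stopping at the first that is not significant, or report them as estimates with 95% intervals.

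Visits, data collection, sample size and ISI power do not change. The cost is that a diary variable alone can no longer be claimed as a primary success. If the sponsor wants all six to keep the primary label, a fixed order starting with ISI also works. An equal alpha split would too, at the power loss shown in the working. The deciding population should be settled separately; this fix does not depend on it.
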